13.3.2.3 Control of Family-wise Type I Error Rate

The **null** hypotheses for the primary efficacy endpoint, **PFS**, and secondary efficacy endpoints (**ORR** and **OS**) will be tested using a fixed sequence hierarchical testing procedure to control the family-wise Type I Error rate below 1-sided 0.025 level. The family of hypotheses is ordered as follows: 1) **PFS**, 2) **ORR**, and 3) **OS**. Starting with the hypothesis of **PFS**, if any hypothesis in the sequence is rejected at a 1-sided significance level of 0.025, then the subsequent hypothesis will be tested; if any hypothesis is accepted, then the subsequent hypotheses will not be tested.

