
Statistical methods and analyses (cont'd):

The hypotheses for the primary efficacy endpoint, **PFS**, and secondary efficacy endpoints (**ORR** and **OS**) will be tested using a fixed sequence hierarchical testing procedure to control the family-wise Type I error rate below 1-sided 0.025 level. The family of hypotheses is ordered as follows: **PFS**, **ORR**, and **OS**. Starting with the hypothesis of **PFS**, if any hypothesis in the sequence is rejected at a 1-sided significance level of 0.025, then the subsequent hypothesis will be tested; if any hypothesis is accepted, then the subsequent hypotheses will not be tested.

Safety analyses will be based on the Safety Population (defined as all randomized subjects who have received at least 1 dose of study treatment). The number and percentage of subjects experiencing 1 or more AEs will be summarized by treatment group, relationship to study treatment, and severity. Changes from baseline and shift in toxicity grade in safety laboratory test results and vital signs will be summarized using descriptive statistics. Adverse events and safety laboratory test results will be graded for severity using the NCI-CTCAE Version 4.03.

Subjects' demographics baseline, and disease characteristics, in addition to prior and concomitant medications and study treatment exposure will be summarized descriptively for each treatment group.

The final PFS analysis will be conducted when approximately 350 PFS events have occurred or by end of year 2018, whichever is earlier. A total of 350 PFS events will provide 83% power to detect a significant difference in PFS between the 2 treatment groups with 1 interim analysis CCI [REDACTED]. The interim analysis will be performed when approximately 75% of the total PFS events (i.e., 263 events) have occurred. The **ORR** and **OS** analyses will be performed at the same time as the primary PFS analysis (interim or final).

TABLE OF CONTENTS

	Page
CLINICAL STUDY PROTOCOL	1
PROTOCOL ACCEPTANCE PAGE	3
SYNOPSIS	4
TABLE OF CONTENTS	12
1 LIST OF ABBREVIATIONS AND DEFINITIONS OF TERMS	19
2 BACKGROUND INFORMATION	23
2.1 Introduction.....	23
2.2 Multiple Myeloma	23
2.3 Proteasome Background	24
2.3.1 Carfilzomib Background (Nonclinical)	24
2.3.2 Carfilzomib Background (Clinical)	25
2.4 Study Rationale.....	27
2.5 Dose Rationale	28
2.5.1 Rationale for Once-weekly Dosing.....	29
2.5.2 Pharmacokinetics and Pharmacodynamics Data for Once-weekly Dosing.....	32
3 STUDY OBJECTIVES	35

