13 STATISTICAL CONSIDERATIONS

This section describes the statistical considerations of the study design and summarizes the statistical analyses that will be conducted to assess the efficacy and safety endpoints in the study. Further details will be provided separately in the Statistical Analysis Plan (SAP). If, after the study has begun, but prior to the final analysis, important changes are made to the primary or key secondary analyses, then the changes will be reflected in the SAP or its amendment where applicable. The study protocol may be amended as appropriate. Any other changes made to the planned analyses after the protocol and SAP have been finalized, along with an explanation as to when and why they occurred, will be described in the clinical study report, in which any post hoc exploratory analyses also will be clearly identified. Any changes made in the analysis plan, after the primary inferential comparisons between treatment groups are performed, will be exploratory in nature.

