13.3.2.2 Secondary Efficacy Endpoints

13.3.2.2.1 Overall Response Rate

The ORR will be analyzed at the time of the PFS analysis (interim or final), only if the PFS analysis crosses the boundary. The inferential comparison of ORR between treatment groups will be made using a logistic regression model-based test against the null hypothesis that the odds ratio is ≤ 1 at a 1-sided significance level of 0.025. The regression model will include the randomization stratification factors as covariates. The ORR will be calculated by treatment group and the associated 95% CI will be estimated using the Clopper-Pearson method. The odds ratio (and its 95% CI) will be estimated using the logistic regression model.

The primary analysis of ORR will be based on the ORCA-assessed responses. Investigator assessed responses will be analyzed as a supportive analysis of ORR, as will IRC-assessed responses.

The duration of response (DOR), defined as time in months from the start date of the response to the earlier date of documented disease progression or death, will be calculated for subjects who achieve sCR, CR, VGPR, or PR. The DOR will be censored at date of the last valid assessment for responders who have not experienced disease progression or death. The distribution of DOR, including the

median, will be estimated using the Kaplan-Meier method on the basis of subjects who achieve overall response.

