10.1 General Principles

[figure not shown]
Continuous variables will be summarized by the non-missing sample size (n), mean, standard deviation, median, minimum, and maximum. Categorical variables will be summarized by the n and percentage in each category. Time to event endpoints will be summarized with Kaplan-Meier (KM) curves, KM proportions at select time points, KM quartiles (when estimable), the number of subjects with events, the number of subjects censored, and censoring reasons. Duration of follow up for time to event endpoints will be estimated using the reverse Kaplan Meier method (Schemper and Smith 1996). Point estimates for efficacy endpoints will be accompanied by 2-sided 95% confidence intervals including estimates of KM quartiles (Klein and Moeschberger, 1997), KM proportions (Kalbfleisch and Prentice, 1980), and binomial proportions (Clopper CJ and Pearson, 1934). To examine non-proportionality between the treatment groups for time to event endpoints, the log cumulative hazard curves will be plotted. The scaled Schoenfeld residuals by time plot will be examined for evidence of a non-zero correlation, which indicates non-proportionality. Interaction between treatment and the log event time will be also tested at 10% level in a Cox model stratified by randomization stratification variables to test for non-proportionality

The hypotheses for the primary efficacy endpoint, PFS, and secondary efficacy endpoints (ORR and OS) will be tested using a fixed sequence hierarchical testing procedure to control the family-wise Type I Error rate below 1 sided 0.025 level. The family of hypotheses is ordered as follows: 1) PFS, 2) ORR, and 3) OS. Starting with the hypothesis of PFS, if any hypothesis in the sequence is rejected, then the subsequent hypothesis will be tested; if any hypothesis is accepted, then the subsequent hypotheses will not be tested. Furthermore, potential multiplicity from testing at two possible times of PFS IA and final analysis for ORR and OS will be adjusted using the Lan-DeMets spending function with an O'Brien-Fleming approach and a Pocock approach respectively (Hung et al 2007).

Statistical Analysis Plan: 20140355

Date: 09 Jun 2017 Page 26

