10.5.2 Analyses of Secondary Efficacy Endpoints

The ORR will be analyzed at the time of the PFS analysis (interim or final), only if the PFS analysis crosses the stopping boundary. The ORR will be calculated by treatment group and the associated 95% CI will be estimated using the Clopper Pearson method. The inferential comparison of ORR between treatment groups will be performed using Cochran-Mantel-Haenszel test stratified by the randomization stratification factors. 1-sided p-value from the test will be compared against the alpha value specified in Table 4 to determine the significance. Odds ratio (and its 95% CI) will be estimated using Mantel-Haenszel method. The primary analysis of ORR will be based on computational assessments for the Primary Analysis Set. Sensitivity analyses will be performed based on investigator assessments, Independent Review Committee (IRC) assessments, unstratified method, and for Per Protocol Set. The discordance between the results from the internal computational assessment, investigator and IRC will be summarized. Subgroup analyses will be performed to explore the consistency of the treatment effect for subgroups described in Section 7.7.

The analysis of OS will be conducted at the time of the PFS analysis (interim or final), only if both PFS and ORR analyses are positive. The same method as for analysis of PFS will be used for analysis of OS. The primary analysis of OS will be performed on the Primary Analysis Set. Sensitivity analyses will be performed based on unstratified analyses, and for Per Protocol Set. Subgroup analyses will be performed to explore the consistency of the treatment effect for subgroups described in Section 7.7. Piecewise Cox models for 6-month time intervals may be explored given evidence of non-proportional hazards.

Statistical Analysis Plan: 20140355

Date: 09 Jun 2017 Page 29

Table 5. Endpoint Summary Table

Endpoint	Primary Summary and Analysis Method	Sensitivity Analysis				
Primary Endpoint						
Progression-Free Survival	Based on internal computational assessments: KM summaries 1-sided p-value from stratified log-rank test Hazard ratio and 95% CI from stratified Cox	 Investigator assessments: same as primary summary and analysis method based on investigator assessments. IRC assessments: Same as primary summary and analysis method based on IRC assessments. 				

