bortezomib refractory in any prior regimen (yes/no), number of prior regimens, Eastern Cooperative Oncology Group (ECOG) performance status, sex, age, race, baseline CrCL, baseline hemoglobin (g/L), baseline serum beta-2 microglobulin (mg/L), and baseline platelet count (<150, ≥150 [10⁹/L]). Additional covariates of interests may be included in the analysis.

11. Changes From Protocol-specified Analyses

In the protocol, it specifies that logistic regression model will be used for ORR analysis. However, since Cochran-Mantel -Haenszel test is more widely used in analysis of binary endpoints to support regulatory filings, Cochran-Mantel-Haenszel test is specified to be used for ORR analysis in the SAP. The CMH test statistic and the score test statistic of the conditional logistic regression are approximately identical (Day N.E.& Byar D.P., 1979), so this analysis method change will not affect the conclusion of ORR analysis.

Statistical Analysis Plan: 20140355

Date: 09 Jun 2017 Page 37

12. Literature Citations / References

Clopper CJ and Pearson ES. The use of confidence or fiducial limits illustrated in the case of the binomial, Biometrika. 1934; 26(4):404-413.

Collett D. Modelling Survival Data in Medical Research. 2nd edition. London, UK: Chapman & Hall/CRC; 2003.

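### Do the flat 0.025 for ORR and OS in the protocol and the alpha spending in the SAP call for a change to the plan?

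*Protocol*

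**What the plan says.** **Protocol.** Section 13.3.2.2.1 tests ORR at the PFS analysis, interim or final, provided PFS has crossed its boundary, against the "null hypothesis that the odds ratio is ≤ 1 at a 1-sided significance level of 0.025". Section 13.3.2.3 orders the hypotheses PFS, ORR, OS and proceeds by the rule "if any hypothesis in the sequence is rejected at a 1-sided significance level of 0.025, then the subsequent hypothesis will be tested"; the synopsis has the same sentence. Section 13.3.2.2.2 puts OS at the same PFS look, conditional on PFS and ORR both being positive, says OS has no interim analysis, and gives no significance level for it. Section 13.8 applies group sequential boundaries to PFS only, and 13.5 describes 0.025 as the overall one-sided error for PFS.

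**SAP.** Section 10.1 repeats the sequence rule without the level: "if any hypothesis in the sequence is rejected, then the subsequent hypothesis will be tested". It then adds that "potential multiplicity from testing at two possible times of PFS IA and final analysis for ORR and OS will be adjusted using the Lan-DeMets" method, O'Brien-Fleming type for ORR and Pocock type for OS. Section 10.5.2 says the ORR p-value "will be compared against the alpha value specified in Table 4 to determine the significance". Section 11 records one departure from the protocol, the replacement of logistic regression by the Cochran-Mantel-Haenszel test, opening with "In the protocol, it specifies that logistic regression model will be used for ORR analysis".

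**Which document carries changes.** Protocol section 13 covers changes decided while the trial is still running: "important changes are made to the primary or key secondary analyses, then the changes will be reflected in the SAP or its amendment". Amending the protocol as well is left as an option.

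**The concern.** Read side by side, the two documents appear to set different pass marks for error-controlled endpoints. The sharpest example is OS at the final analysis. A one-sided p of 0.018 succeeds if 0.025 applies and fails under the SAP, whose Pocock-type final level lies between about 0.012 and 0.014 for any OS information fraction from 0.5 to 0.95. For ORR, the O'Brien-Fleming-type level at the interim could be as low as 0.0097 if the information fraction were 0.75.

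Two further points sharpen the worry. SAP section 11 lists a change of ORR test that it says will not affect the conclusion, yet omits a change of threshold that could. And the flat rule, taken literally, does not quite hold 0.025 for OS, because OS can be tested at either of two looks and the look is chosen by a correlated endpoint. If the pass mark for OS were argued over only after unblinding, any choice would look driven by the data.

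**Working it through.** **Inputs.** From the documents: one-sided alpha 0.025; PFS looks at 263 and 350 events, so t = 263/350 = 0.7514; 1:1 allocation; stated power 83%. Assumed: PFS hazard ratio 0.73, because the current value is redacted and 0.73 appears only in superseded text in the amendment summary; OS information fraction 0.75; ORR taken as passed. The values in SAP Table 4 are not visible in the copy read, so none are used.

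**1. The plan's own figure.**
- O'Brien-Fleming-type spending: α(t) = 2[1 − Φ(2.2414/√t)] = 2[1 − Φ(2.2414/0.8668)] = 0.0097, so z = 2.337 at the interim.
- Solving P(Z₁ < 2.337, Z₂ > c) = 0.025 − 0.0097 with correlation √t = 0.8668 gives c = 2.012, a final level of 0.0221.
- Drift at HR 0.73: √350/2 × |ln 0.73| = 9.354 × 0.3147 = 2.944.
- P(cross at interim) = 1 − Φ(2.337 − 2.944 × 0.8668) = 58.5%. Over both looks it is 83.1%, which reproduces the stated 83%. PFS crosses only at the final look in 83.1 − 58.5 = 24.6%.

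**2. SAP-type levels for the secondary endpoints.** Pocock-type spending is α(t) = 0.025 × ln[1 + (e − 1)t].
- OS at fraction 0.75: 0.025 × ln(1 + 1.7183 × 0.75) = 0.0207 at the interim; the bivariate normal solution gives 0.0120 at the final.
- OS final level at fractions 0.5, 0.6, 0.7, 0.8, 0.9, 0.95: 0.0139, 0.0129, 0.0122, 0.0119, 0.0125, 0.0138.
- ORR interim level at fractions 0.90, 0.95, 0.99: 0.0181, 0.0215, 0.0243. If response data are nearly complete at the interim, the ORR level is close to 0.025 anyway.

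**3. How often the rules would disagree on OS.** This was simulated with 150 to 300 deaths, OS HR 0.70 to 0.82 and PFS-OS correlation 0.3 to 0.7. PFS crosses only at the final and the OS verdicts differ in 1.6 to 3.8% of trials; at the interim the figure is 0.9 to 2.1%; in total, 3.3 to 5.8%. These are upper values because ORR is assumed to pass. They also depend on the PFS effect. For the cases with 245 and 250 deaths at correlation 0.5, final-look disagreement is 2.3 to 3.3% at PFS HR 0.73, 0.6 to 1.2% at HR 0.65 and 0.1 to 0.3% at HR 0.60.

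**4. Which rule controls the error.** OS type I error = P(PFS crosses at look 1 and OS significant) + P(PFS crosses only at look 2 and OS significant), computed with OS null and OS fraction 0.75.

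| PFS-OS correlation | Flat 0.025, PFS HR 0.73 | Flat 0.025, worst PFS effect | SAP Pocock type, worst PFS effect |
|---|---|---|---|
| 0.3 | 0.0247 | 0.0252 | 0.0207 |
| 0.5 | 0.0256 | 0.0256 | 0.0207 |
| 0.7 | 0.0254 | 0.0266 | 0.0208 |

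The flat rule overshoots slightly; the SAP rule does not.

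**5. Reading the texts together.** The 0.025 in Protocol 13.3.2.3 covers all three hypotheses, starting with PFS. For PFS it cannot be a per-look level, because 13.8 gives PFS its own spending boundary. The sentence can therefore be read as an overall level for each hypothesis, and for OS nothing else in the protocol says otherwise. On that reading the SAP supplies a split that the protocol left open. Only for ORR does 13.3.2.2.1 tie 0.025 directly to the test, so only there is the conflict plain.

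**The case for a change.** The strongest case for acting is that a section headed as the list of changes from the protocol should be complete, and a threshold that can reverse a verdict matters more than a swap between near-equivalent tests. The OS example needs neither Table 4 nor an assumed effect size: p = 0.018 at the final look separates the two rules for any OS fraction from 0.5 to 0.95. The remedy in the SAP would be one entry, made before unblinding.

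Most of that is fair as a comment on record-keeping. Section 11 is incomplete, and for ORR the difference from the protocol is real. What does not stand is the step from there to two competing decision rules. A reader of SAP 10.1 and 10.5.2 is told what will be done, and Protocol section 13 names the SAP as the place for such a change. The SAP, dated 09 Jun 2017, follows the protocol amendment of 07 March 2017. The stricter rule is the one in force, so nobody could claim success under a looser standard without setting aside the later document. Rewriting the protocol would not be free either: section 15.1 sends substantive amendments to health authorities and ethics committees, and about 150 sites are planned, for a text that the SAP already overrides.

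**Conclusion.** No change to the plan is needed. The wording differs and the arithmetic behind the difference is sound, but an analyst who follows the SAP applies a stated two-look spending rule. In the cases checked that rule holds the OS type I error to about 0.021, below the 0.025 limit. The small excess of the flat rule, at most 0.0266 for correlations up to 0.7, belongs to wording that is not operative.

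The residue is a clerical omission in SAP section 11: firm for ORR, where the gap shrinks towards nothing as response data near completion at the interim, and arguable for OS, where the protocol sentence can be read as an overall level. Recording it would tidy the file and leave every threshold, analysis and conclusion as it is.

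The disagreement figures (3.3 to 5.8% in total) rest on PFS HR 0.73, an OS fraction of 0.75, the stated ranges for deaths, OS effect and correlation, and ORR always passing. The conclusion does not depend on them. It rests on the SAP being the later and governing text, and on its rule being the one that controls the error.

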13.3.3 SAFETY ANALYSIS

Safety analyses will be based on the Safety Population (defined as all randomized subjects who have received at least 1 dose of study treatment).

13.3.3.1 Adverse Events

Treatment-emergent adverse events are defined as AEs that start on or after the first day study treatment is administered and within 30 days of the last administration of study treatment. The reported AE term will be coded using MedDRA and will be graded for severity using NCI-CTCAE Version 4.03. The causal relationship between the occurrence of an AE and each treatment will be assessed by the investigator as related or not related.

Treatment-emergent adverse events will be summarized based on the number and percentage of subjects experiencing events by treatment group and by MedDRA system organ class (SOC) and preferred term. In the event that a patient experiences repeated episodes of the same AE, the subject will be counted once within each SOC and similarly counted once within each preferred term and the event with the highest severity grade and/or strongest causal relationship to each treatment will be used for purposes of incidence tabulations.

Tabular summaries of the following will be provided:

- All TEAEs by SOC
- All TEAEs in decreasing order of frequency
- TEAEs by causal relationship to study drug
- TEAEs by maximum severity grade
- All SAEs by SOC
- All SAEs in decreasing order of frequency
- TEAEs resulting in modification (i.e., dose reduction or dose interruption) of study treatment
- TEAEs resulting in discontinuation of study treatment
- Deaths within 30 days of the last administration of study treatment
- All AEs, including TEAEs, will be included in individual patient listings.

13.3.3.2 Safety Laboratory Values

For hematology, chemistry, and other laboratory values, the baseline values, changes from baseline by visit, the minimum, maximum, and last observed values will be summarized descriptively.

For the summary of changes from baseline by visit, subjects without a baseline and/or post baseline value will be excluded; values from unscheduled assessments will be excluded. Subjects with missing data for a scheduled assessment time point will be excluded from the summary for that time point. Laboratory results from samples taken > 30 days after the last administration of protocol therapy will be excluded from the laboratory summaries.

All available laboratory data, including those excluded from summary tabulations, will be included in individual patient listings.

Laboratory test results will be graded using the NCI-CTCAE (Version 4.03). Shifts in laboratory toxicity grades to outside the normal range will be evaluated for selected laboratory parameters by assessing the maximum increase and/or decrease observed during the course of study treatment relative to the baseline toxicity grade.

The subject incidence of Grade 3 and 4 hematological laboratory abnormalities (including neutropenia, thrombocytopenia, and anemia) will be provided by treatment group.

The subject incidence of Grade 3 and 4 nonhematological laboratory abnormalities (including liver function test [LFT], CrCl) will be provided by treatment group. Similar analyses will be done for selected chemistry tests.

13.3.3 Vital Signs

Vital sign results (systolic and diastolic blood pressure, pulse, respiratory rate, and temperature) will be summarized descriptively for baseline values and changes from baseline to the minimum, maximum, and last observed values.

For the summary of changes from baseline by visit, subjects without a baseline and/or past-baseline value will be excluded; values from unscheduled assessments will be excluded. Vital sign results taken > 30 days after the last administration of protocol therapy will be excluded from all vital sign summaries.

13.3.4 *SPARSE PHARMACOKINETIC ANALYSES*

A sparse PK sampling strategy will be employed in this study, at a subset of study sites. Blood samples will be collected at specified times, processed and stored until analysis. Concentrations of carfilzomib will be measured in plasma using a validated assay method.

The population pharmacokinetic analysis will be a cumulative analysis that will include population pharmacokinetic data obtained from previous Phase 2 and Phase 3 studies that

used intensive or sparse PK sampling. The analysis plan as well as a stand-alone pharmacokinetic analysis report will be prepared separately. The population modeling program may be used to fit a nonlinear mixed effects model to estimate PK parameters, including clearance and volume of distribution, the inter- and intra-subject variability, and the population variability in the parameter estimates. The PK concentrations obtained from subjects who participate in the sparse PK sampling, along with results from the intensive PK/PDn substudy and other carfilzomib studies, will be used in the development of a structural model. The best model will be evaluated by goodness-of-fit statistics and reduction in the objective function and posterior predictive checks. Subject characteristics such as age, gender, body weight, BSA, and race will be included in the model to identify potential covariates affecting PK of carfilzomib.

Additional analyses may be performed to evaluate the relationship between the estimated PK parameters and selected safety or clinical effect endpoints.

